3.2.1.5 Multicenter Studies

This study expects to enroll approximately 135 patients from 30 to 35 investigative sites. For analyses that include investigative site, the analysis will use pooled sites. All sites with fewer than two randomized patients per treatment group with non-missing baseline and Week 66 mNIS+7 composite scores will be pooled together within country and considered a single site for analysis. If

this results in any site with fewer than two randomized patients per pooled site, the smallest site will be pooled with the next smallest site within the same geographic region (North America, Europe, or South America/Australasia). If there are no other sites in the region, no further pooling will be conducted.

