- A variety of multiple imputation methods will be used to investigate the impact of different patterns of missing data

- Addition of pooled investigative site to the primary efficacy MMRM model, where pooled site will be specified in the SAP prior to unblinding. The interaction between treatment and pooled site will be examined if model convergence permits
- Responder analysis (for mNIS+7 only) to examine if the improvement in response is consistent over a range of response thresholds. If a patient terminates treatment early due to AE or lack of efficacy or other types of treatment failure, then the response of the patient is considered as non-responder. Other missing values are considered as censoring
 - For the set of response thresholds, the proportion of responders will be plotted against the responder threshold by treatment group

Secondary efficacy analyses include:

- Comparison of change from baseline to Week 66 in the Norfolk QOL-DN questionnaire symptoms domain score (Stage 1 patients) and Norfolk QOL-DN questionnaire physical functioning/large fiber neuropathy domain score (Stage 2 patients) between ISIS 420915 300 mg and placebo group in the Full Analysis Set
- Comparison of change from baseline to Week 65 in mBMI and BMI between ISIS 420915 300 mg and placebo group in the Full Analysis Set
- Comparison of change from baseline to Week 66 in the NIS, modified +7, and NIS+7 between ISIS 420915 300 mg and placebo group in the Full Analysis Set. Comparison of change from baseline to Week 66 in Norfolk QOL-DN domain scores (symptoms domain for Stage 1 patients and physical functioning/large fiber neuropathy domain for Stage 2 patients), NIS, modified +7 and NIS+7, and change from baseline to Week 65 in mBMI and BMI between ISIS 420915 300 mg and placebo group in the Per-Protocol Set
- Comparison of change from baseline to Week 65 in GLS by ECHO in the ECHO subgroup and in the CM-ECHO Set

Tertiary analyses include:

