- **Sensitivity Analysis 8 (Per Protocol Set)** – The primary efficacy analysis will be repeated, using the PPS population.

- **Sensitivity Analysis 9** (Adjustment for Pooled Site) – The primary efficacy analysis will be repeated, but with the addition of pooled investigative site as a fixed categorical effect in the model. In the event that there are model convergence issues, results from this analysis will not be provided and will be noted in the study report. The interaction between treatment and pooled site will also be examined if model convergence permits.
- **Sensitivity Analysis 10** (Responder Analysis) – A responder analysis based on the change in mNIS +7 score will be conducted to examine whether improvement in response is consistent over a range of response thresholds. A responder is defined as a patient whose mNIS +7 score change from baseline to Week 66 is less than or equal to the threshold value. The relationship between response rate and thresholds will be summarized using a cumulative distribution plot. In addition, comparison of response rates for specific threshold values will be done. Thresholds that will be tested will include 0, 2, 4, 6, 8, 10, 15, 20, 30 points above the baseline value. For each of these specific response thresholds, the response rates at Week 66 for both the treated group and the placebo group will be calculated and plotted against the response threshold. Patients that terminate treatment early irrespective of the reason or had missing Week 66 data will be considered a non-responder. The difference in the estimated response rate and associated 95% CI based on the Mantel-Haenszel approach will be presented for each threshold.
- **Sensitivity Analysis 11** (HRDB and Nerve Conductions Scored Using Points and NIS-Sensation Excluded) – Additional sensitivity analysis on mNIS+7 composite score will be performed using the points (instead of Normal Dev) from heart rate deep breathing and nerve conduction and also removing the sensation part of the NIS.
- **Sensitivity Analysis 12** (HRDB Component Excluded) – Additional sensitivity analysis on mNIS+7 composite score will be performed, with HRDB not included as a component. HRDB will also be descriptively summarized for the group that has least one non-imputed HRDB score during efficacy treatment period and a non-imputed score at baseline.

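### The second site-pooling step in SAP 3.2.1.5 drops the per-arm condition, so a pooled site with patients in only one arm can remain in Sensitivity Analysis 9

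*SAP*

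**What the plan says.** SAP 3.2.1.5 (Multicenter Studies) sets out a two-step rule.

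- Step 1, within country: "All sites with fewer than two randomized patients per treatment group with non-missing baseline and Week 66 mNIS+7 composite scores will be pooled together" and treated as one site.
- Step 2, within region: if "this results in any site with fewer than two randomized patients per pooled site", the smallest is merged with the next smallest in the same region. The rule ends with "If there are no other sites in the region, no further pooling will be conducted".

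The pooled sites are used in Sensitivity Analysis 9 (SAP 3.3.3). It repeats the primary MMRM "with the addition of pooled investigative site as a fixed categorical effect in the model". If the model has convergence problems, the results are not provided and the report says so. "The interaction between treatment and pooled site will also be examined if model convergence permits".

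Protocol 10.5.3 lists the same sensitivity analysis, "where pooled site will be specified in the SAP prior to unblinding". The SAP gives the expected size ("This study expects to enroll approximately 135 patients from 30 to 35 investigative sites") but not the number of countries or the patients per country.

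**The concern.** The two steps apply different standards. Step 1 asks for two patients in each arm with data. Step 2 decides whether the country pools that result are adequate, and it asks only for two randomized patients in total. Two patients in the same arm pass, and so does a pool with no Week 66 data. The standard is dropped where it is most needed, because most single sites will fail step 1 and end up in a country pool.

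Sensitivity Analysis 9 is the only listed analysis that adjusts the primary endpoints for site. A one-arm pooled site gives no within-site treatment comparison to the main-effect model and leaves an empty cell in the interaction model. A model with an empty cell can converge and still have non-estimable contrasts, and the SAP does not say what is reported then.

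**Working it through.** **Plan's own figures.** The pooling rule carries no figure. The power statements in SAP 4 use 135 patients at 2:1 with 25% dropout, so 45 × 0.75 = 33.75 placebo and 67.5 active. With √(1/33.75 + 1/67.5) = 0.2108:
- mNIS+7: 9.6/(14 × 0.2108) − 1.96 = 1.29, power 0.902 (stated: at least 90%).
- Norfolk QOL-DN: 10.7/(18 × 0.2108) − 1.96 = 0.86, power 0.805 (stated: at least 80%).

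Neither calculation involves site.

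**Site size.** 135/30 = 4.5 and 135/35 = 3.9 patients per site. After 25% dropout this is 3.4 and 2.9 with Week 66 data, of whom 33.75/30 = 1.13 and 33.75/35 = 0.96 are on placebo. A site with four patients, all with data, still has fewer than two in some arm with probability 0.70. Most sites therefore go into country pools.

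**Chance that a pool is one-armed.** The randomization strata in SAP 2.2 are three patient-level factors, so balance within site is not protected. Treating assignments within a pool as independent (an approximation; the block size is in a separate document), P = (2/3)^n + (1/3)^n:
- n = 2: 4/9 + 1/9 = 0.556
- n = 3: 8/27 + 1/27 = 0.333
- n = 4: 16/81 + 1/81 = 0.210
- n = 8: 0.039

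**Chance that at least one such site remains.** The literal rule was simulated for 135 patients (90:45) in 30 and 35 sites. The number of countries, uneven site and country sizes, three regions and 25% Week 66 data missing at random are assumptions. There were 1,000 trials per layout, and 500 for the last column. Ranges cover 30 and 35 sites.

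| Countries | One-arm by randomization | An arm without Week 66 data | One-arm by randomization, step 1 criterion reused at step 2 |
|---|---|---|---|
| 3 | 11-13% | 22-23% | 3-4% |
| 5 | 33% | 51-54% | 6-7% |
| 8 | 58-61% | 81-84% | 6-8% |
| 10 | 74% | 91-92% | 5-7% |
| 12 | 81-82% | 95-96% | 6% |
| 15 | 91% | 98-99% | 5-7% |

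The second column is the closer guide. Sensitivity Analysis 9 uses Week 35 and Week 66 data and has no site-by-time term, so a Week 35 value is enough to fill a cell. A separate run that counted arms with neither Week 35 nor Week 66 data gave about 13% with 3 countries and about 90% with 15.

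**Main-effect model.** Illustrative layout: 64 active and 34 placebo in two-arm sites, plus 7 patients in three one-arm sites. A Week 35 SD of 11 and a correlation of 0.3 to 0.8 are assumed. Compared with leaving the 7 patients out:
- kept as one-arm sites, the variance of the Week 66 contrast is multiplied by 0.969 to 0.977 (a fall of 2.3-3.1%);
- merged into a two-arm site, it is multiplied by 0.939 (a fall of 6.1%).

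The patients keep about 2.3/6.1 = 38% to 3.1/6.1 = 51% of the gain. Variance is 0.969/0.939 = 1.03 to 0.977/0.939 = 1.04 times what merging would give, or about 2% in standard error.

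**Interaction model.** Eight two-arm sites fill 16 cells, the interaction has 7 degrees of freedom, and the site-averaged treatment difference is estimable. Adding two one-arm sites gives 18 filled cells out of 20. The interaction has 18 − (1 + 1 + 9) = 7 degrees of freedom, unchanged, but the treatment difference averaged over all ten sites is no longer estimable.

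**The case against.** The case for leaving the rule alone has real force.

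- **Little is lost.** A reader might infer that patients in one-arm sites drop out of the analysis. They do not. Site is not crossed with time, so they still inform the treatment-by-time, covariate and covariance terms. This stands.
- **The interaction can still be examined.** A reader might infer that empty cells prevent it. The test across two-arm sites is unaffected, and the SAP promises no site-averaged estimate from that model. This stands. What is lost is narrower: the effect in the one-arm sites and the average over all sites.
- **Merging has a price.** Combining sites from different countries gains precision by assuming a common site effect, which means adjusting less for site. This is a fair trade-off, but step 1 has already set the per-arm standard, and the SAP gives no reason to relax it at step 2.
- **The frequency rests on unseen inputs.** With about three countries a one-arm site is uncommon. This stands. Counting arms without Week 66 data would also overstate the problem, for the reason given in the working.
- **Step 2 may have been meant per arm.** Possibly, but the text does not say so.

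A reader might also infer a conflict with Protocol 10.5.3, because step 1 needs treatment codes and Week 66 availability. The documents do not support that. The Protocol asks for pooled site to be specified in the SAP before unblinding. A mechanical rule in a SAP finalized before unblinding (SAP 2.6) meets this, and membership need not be listed by then.

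**Conclusion.** The point holds in limited form. On its wording, step 2 can leave pooled sites with patients in only one arm. How often depends on the number of countries: about 10-15% of trials with 3 and about 60-90% with 8 to 15, under assumed site sizes, regions and missingness.

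In the illustrative layout, the cost to the main-effect version of Sensitivity Analysis 9 is a variance about 3-4% higher than with merging. In the interaction version, two quantities become non-estimable and the fallback does not cover that case.

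The primary MMRM (SAP 3.3.2) has no site term, so the primary result, the alpha and the power do not change. Regional differences are also examined in the subgroup analyses (SAP 3.3.4). This is an inexpensive improvement to one sensitivity analysis.

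**What to change.** In SAP 3.2.1.5, apply the step 1 criterion at step 2 as well: at least two patients per treatment group with the required data. Repeat the merging within region until every pooled site meets it or no other site remains in the region. Keep the with-data condition; counting randomized patients instead would again admit arms without data.

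In Sensitivity Analysis 9, extend the fallback from non-convergence to non-estimable contrasts, and say what is reported when a cell is empty. This is still needed, because a region with no other site can leave a one-arm pool: in the simulation, 3-8% of trials still had one.

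The cost is two wording changes and coarser pooled sites in one sensitivity analysis. The simulated average number of pooled sites goes from about 9-18 to about 9-11.

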3.2.2 Subject Populations Analyzed

The following analysis populations are defined for this study:

- Screened patients will be defined as those patients who signed an informed consent form.
- The Randomized Set will be defined as those screened patients who received a randomization assignment. Results will be summarized under the treatment to which patients were randomized.
- The Full Analysis Set (FAS) will include all randomized patients who received at least 1 injection of Study Drug (ISIS 420915 or placebo) and who have a baseline and at least one post-baseline efficacy assessment for the mNIS+7 score or Norfolk QOL-DN questionnaire total score. This will be the primary population for analysis of efficacy and PD outcomes. Results will be summarized under the treatment to which patients were randomized.
- The Safety Set (SS) will include all randomized patients who received at least 1 injection of Study Drug. This population will be used for analyses of all safety measures. Results will be summarized under the treatment which the patients received.
- The Per-Protocol Set (PPS) will include the subset of the Full Analysis Set who have received at least 80% of the prescribed doses of Study Drug and who have no major protocol violations that would be expected to affect efficacy assessments. Prescribed doses of Study Drug mentioned above is defined as the total assigned dose in mg from the Week 1 to the last dose within this study, i.e. $300\text{mg} \times 67\text{doses} = 20100\text{mg}$. This will be a secondary population for efficacy and PD analyses and will be used for sensitivity purposes. The detailed criteria and definitions for major protocol violations will be specified and finalized prior to unblinding; individual subjects will be identified as meeting the violation criteria or not after locking the database and prior to unblinding. Results will be summarized under the treatment which the patients received.
- PK Set will include all subjects who are randomized and receive at least one dose of active Study Drug (ISIS 420915) and have at least one evaluable PK sample collected and analyzed with reportable result. Results will be summarized under the treatment which the patients received.
- The Pharmacokinetic subgroup (PKS) will include the patients that participated in the PK subgroup who have at least one evaluable PK result. This population will be used for pharmacokinetic analyses. Results will be summarized under the treatment which the patients received.

- The ECHO subgroup will include the subset of the Randomized Set that and qualified and consented for the ECHO substudy. Results will be summarized under the treatment to which patients were randomized.
- The CM-ECHO Set will include the subset of the Randomized Set that meet at least one of the following criteria, 1) diagnosis of TTR cardiomyopathy at study entry, or 2) eligible to participate in the ECHO subgroup (whether consented or not). Results will be summarized under the treatment to which patients were randomized.
- The TTR subgroup will consist of the subset of the Safety Set who have completed their Week 13 visit and are included in the interim analysis of TTR. Results will be summarized under the treatment to which patients were randomized.

All primary, secondary (except GLS), and PD endpoints will be assessed on the Full Analysis Set and Per-Protocol Set, with the former being the basis for the primary efficacy analysis. All safety assessments will be performed on the Safety Set. PK endpoints will be assessed in the PK Set as applicable.

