10.3 Populations

The Full Analysis Set will include all randomized patients who received at least 1 injection of Study Drug (ISIS 420915 or placebo) and who have at least 1 post-baseline efficacy assessment for the mNIS+7 score or Norfolk QOL-DN questionnaire total score.

The Safety Set will include all randomized patients who received at least 1 injection of Study Drug.

The Per-Protocol Set will include the subset of the Full Analysis Set that have received at least a certain percentage of the prescribed doses of Study Drug and that have no significant protocol deviations that would be expected to affect efficacy assessments. The detailed criteria will be specified and finalized prior to conducting the primary analysis (i.e., exact criteria to determine inclusion in or exclusion from the Per Protocol Set will be determined for each patient prior to conducting the primary analysis).

The Pharmacokinetic Set will include the subset of the Safety Set that has at least 1 evaluable PK result.

The ECHO subgroup will include the subset of the Safety Set that has at least 1 evaluable post baseline ECHO assessment and participated in the ECHO substudy. The CM-ECHO Set will include the subset of the Safety Set that has at least 1 evaluable post baseline ECHO assessment and had a diagnosis of TTR cardiomyopathy at study entry but are not in the ECHO subgroup, plus patients who participated in the ECHO subgroup.

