3.4.1 Secondary Efficacy Endpoint Definitions

Secondary efficacy endpoints are:

- Change from baseline to Week 66 in the Norfolk QOL-DN questionnaire symptoms domain score (Stage 1 patients only) and the Norfolk QOL-DN questionnaire physical functioning/large fiber neuropathy domain score (Stage 2 patients only)
- Change from baseline to Week 65 in the Modified Body Mass Index (mBMI)
- Change from baseline to Week 65 in the Body Mass Index (BMI)
- Change from baseline to Week 66 in the NIS
- Change from baseline to Week 66 in the modified +7

- Change from baseline to Week 66 in the NIS+7
- Change in GLS by ECHO from baseline to Week 65 in the Randomized Set, ECHO subgroup and in the CM-ECHO Set

Treatment group differences will be evaluated using the same method as the primary efficacy analysis (MMRM described in Section 3.3.2). These analyses will be conducted on both the FAS and the PPS populations. The analysis for GLS will be specified in the ECHO SAP.

The normality assumptions for the MMRM will be assessed for each of the secondary endpoints by inspecting the following plots:

- Histogram of marginal studentized residuals derived from the MMRM model.
- Normal probability plot.

The non-parametric Van-Elteren test may be performed as a sensitivity analysis, if deemed necessary. Hodges-Lehmann estimates of the differences between ISIS 420915 300 mg group and the placebo group as well as distribution-free confidence intervals based on the Wilcoxon Rank Sum Test will also be provided.

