3.4.2 Pharmacodynamic Endpoint Definitions

Pharmacodynamic endpoints are:

- Change and percent change from baseline to Week 65 in TTR level
- Change and percent change from baseline to Week 65 in RBP4 level.

Analyses of the pharmacodynamic endpoints will be evaluated using the same method as the primary efficacy analysis (MMRM described in Section 3.3.2). All pharmacodynamic analyses will be conducted on both the FAS and the PPS.

In addition the proportion of subjects with percentage decrease from baseline in plasma transthyretin (TTR) $\geq 60\%$ will be summarized by treatment group at each visit.

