3.6 Exploratory Analyses

Exploratory endpoints include the following:

- Change from baseline in echocardiogram parameters (except GLS) in the Randomized Set, ECHO subgroup and in the CM-ECHO Set
- Change and percent change from baseline in NT-proBNP in the FAS, ECHO subgroup and in the CM-ECHO Set
- Change from baseline in the log-transformed NT-proBNP values in the FAS, ECHO subgroup and in the CM-ECHO Set
- Shift table from baseline in PND score in the FAS and in the PPS
- Change from baseline in NSC total score in the FAS and in the PPS
- Change from baseline in the NSC individual domain scores (muscle weakness, sensory [hypo/loss of sensation], sensory [paresthesia, hyper sensation], autonomic [GI/urinary incontinence], and autonomic [other than GI//urinary incontinence]) in the FAS and in the PPS
- Proportion of patients with at least 60% reduction in TTR in the FAS and in the PPS

Echocardiogram parameters, NSC (total and individual domains), and NT-proBNP (log-transformed) will be summarized and statistically analyzed using the MMRM described in Section 3.3.2. Summary statistics will be used to summarize the other exploratory endpoints.

Note that the 7 point change score (-3, -2, -1, 0, 1, 2, 3) that is recorded on the NSC questionnaire will be listed but not summarised or analysed. Similarly for questions 20-29 the location is only listed. Questions 31-34 are of particular interest and therefore the number and percentage of patients responding 0 (No), 1 (slight +), 2 (moderate ++) or 3 (severe +++) will be presented.

The ECHO data analysis will be conducted by CICL.

Note: retinol and retinyl palmitate are specified as exploratory endpoints in the protocol. These endpoints are considered safety endpoints and therefore will be summarized with safety laboratory parameters.

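### Dosed patients who leave before Week 35 with no early-termination mNIS+7 or Norfolk QOL-DN are excluded from the TTR, RBP4, BMI and mBMI analyses and the FAS analysis of NT-proBNP, even when those endpoints were measured

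*SAP*

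**What the plan says.** **The gate.** SAP 3.2.2 restricts the FAS to dosed, randomised patients "who have a baseline and at least one post-baseline efficacy assessment for the mNIS+7 score or Norfolk QOL-DN questionnaire total score". Protocol 10.3 has the same gate without the explicit baseline condition: patients "who have at least 1 post-baseline efficacy assessment for the mNIS+7 score or Norfolk QOL-DN questionnaire total score".

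**Where the set is used.** SAP 3.2.2 continues: "This will be the primary population for analysis of efficacy and PD outcomes". For TTR and RBP4, SAP 3.4.2 states: "All pharmacodynamic analyses will be conducted on both the FAS and the PPS". For the secondary endpoints, including BMI and mBMI, SAP 3.4.1 states: "These analyses will be conducted on both the FAS and the PPS populations". The Per-Protocol Set (PPS) is a subset of the FAS, so it carries the same gate. SAP 3.6 places the 60% TTR reduction proportion in the FAS and PPS. It lists NT-proBNP as "Change and percent change from baseline in NT-proBNP in the FAS, ECHO subgroup and in the CM-ECHO Set". The last two of those sets do not depend on mNIS+7 or Norfolk QOL-DN. For example, SAP 3.2.2 says: "The CM-ECHO Set will include the subset of the Randomized Set that meet at least one of the following criteria".

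**Timing.** SAP 2.1 schedules mNIS+7 and Norfolk QOL-DN at baseline, Week 35 and Week 66. It has TTR, RBP4, BMI, mBMI and NT-proBNP measured periodically on treatment. Patients who stop treatment early are to have both instruments within 14 days of the last dose (SAP 2.1) or, failing that, as soon as possible (Protocol 6.1.3).

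**The concern.** FAS entry turns on whether a different instrument was completed later, not on whether the analysed endpoint was measured. A patient can have several valid TTR values and still be left out because no mNIS+7 or Norfolk QOL-DN followed.

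The early-termination assessment narrows this gap but does not close it. Protocol 8.8 asks for every effort, which is not a guarantee. Protocol 8.9 ends observation at once when consent is withdrawn and only encourages a final assessment. A patient who dies cannot attend; the Amendment 9 summary records a fatal intracranial bleed in this study, with arm and timing not stated.

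Exclusion therefore follows post-randomisation events that may differ between arms. At stake are the by-visit TTR proportions before Week 35, which would describe only patients known to have been assessed later, and early-visit values that the MMRM could otherwise use. BMI and mBMI are secondary endpoints evaluated at a two-sided 0.05 level (SAP 3.2.1).

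**Working it through.** **The plan's own figure.** The point does not dispute the sample size, but the plan's inputs are used below, so they were checked first. With 135 patients, 2:1 allocation and 25% dropout, 33.75 placebo and 67.5 active patients are evaluable.

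- mNIS+7: SE = 14 × √(1/33.75 + 1/67.5) = 2.95; 9.6/2.95 − 1.96 = 1.29; power 90.2% (89.6% with the noncentral t).
- Norfolk QOL-DN: SE = 18 × √(1/33.75 + 1/67.5) = 3.79; 10.7/3.79 − 1.96 = 0.86; power 80.5% (79.7% with the noncentral t).

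The stated power is reproduced and does not depend on this point.

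**Inputs from the documents.**

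- 135 patients and 25% dropout (SAP section 4).
- Last dosing visit on Day 449 (Protocol Appendix A).
- Week 35 window opening on Day 209. This comes from section 3.1.3 of the DSMB analysis plan appended to the SAP, because the main SAP windows are redacted.
- TTR and RBP4 draws at Weeks 3, 5, 8, 13, 18, 23 and 29. The PD panel row of Appendix A follows the PK trough row after screening, and Appendix C dates the troughs.
- Body weight and NT-proBNP: as far as the broken Appendix A table can be read, about one scheduled on-treatment value before Week 35.

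**Assumptions not in the documents.**

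- Constant dropout hazard.
- A patient stopping before Day 195 to 202 (14 to 7 days before Day 209) has no Week 35 value.
- The single early weight and NT-proBNP value is taken at Day 85.
- Between 25% and 100% of early leavers lack both instruments at early termination.

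**Step 1: early leavers.** λ = −ln(0.75) = 0.2877 over 449 days.

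- P(stop before Day 195) = 1 − exp(−0.2877 × 195/449) = 11.7%.
- P(stop before Day 202) = 1 − exp(−0.2877 × 202/449) = 12.1%.
- 135 × 11.7% to 12.1% = about 16 patients.

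**Step 2: TTR and RBP4.** 25% to 100% of 16 gives about 4 to 16 patients outside the FAS. This is slightly generous: 135 × [1 − exp(−0.2877 × 15/449)] = 1.3, so about one of the 16 stops before the first post-dose draw on Day 15 and has no value to lose.

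**Step 3: BMI, mBMI and NT-proBNP.** Only patients who stop after the Day 85 value have something to lose, if those without the efficacy assessment also lack the rest of the early-termination visit.

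- P(still on treatment at Day 85) = exp(−0.2877 × 85/449) = 94.7%.
- P(stop between Day 85 and Day 195 to 202) = 94.7% − 88.3% to 94.7% − 87.9% = 6.4% to 6.8%.
- 135 × 6.4% to 6.8% = about 9 patients; 25% to 100% of these gives about 2 to 9.

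**Cross-check for Step 2.** With dropout uniform over 65 weeks, 34/65 = 52% of dropouts leave before Week 35. Then 135 × 0.25 × 0.523 = 17.7 patients; 25% of these is 4.4. The two dropout shapes agree closely. If every early leaver is assessed, the count is zero under either.

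**Comparison within the plan.** The SAP's PK Set requires an evaluable result of its own endpoint. The TTR interim set is a subset of the Safety Set. Sensitivity Analyses 4 to 7 use the Safety Set, but only for the two primary endpoints (SAP 3.3.3). TTR, RBP4, BMI and mBMI have no such counterpart.

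**The case against.** The strongest reply is that the gate is easy to pass. Both instruments are planned for every early terminator and either one suffices. The FAS definition sets no visit window, and the rerandomization steps in SAP 3.3.2 confirm that FAS patients may have only out-of-window data. A reader might infer that dosed patients who leave early are dropped as a class. The documents do not support that: only those with neither instrument after baseline are lost. This part of the objection stands and limits the point. The upper end of each range, where no early leaver completes even the questionnaire, is a bound and not an expectation.

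A reader might also infer that early decliners vanish from the weight and cardiac data. They do not. Body weight is summarised by visit and arm on the Safety Set (SAP 3.9 and 3.9.3), though without a treatment comparison. NT-proBNP is exploratory and is also analysed in two sets without the gate. FAS and Safety Set counts will be reported by arm and all data listed, so exclusions will be visible.

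Finally, the named PD, BMI and mBMI endpoints are changes to Week 65. Patients who leave before Week 35 have no on-treatment Week 65 value in any population, so restoring them adds only what their early values predict. That is correct. The gain is mainly in the early by-visit summaries and in the early data entering the model.

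**Conclusion.** The point holds in a narrow form. It concerns dosed patients who leave before Week 35 with no post-baseline mNIS+7 or Norfolk QOL-DN. Their on-treatment values are discarded from the TTR, RBP4, BMI and mBMI analyses and from the FAS analysis of NT-proBNP, under a rule unrelated to those endpoints.

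The sizes in the working depend on the assumed constant hazard, the assumed Day 85 timing and, above all, the unknown share of early leavers who go unassessed.

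The mNIS+7 and Norfolk QOL-DN analyses are unaffected. The overall TTR conclusion is unlikely to change, since Protocol 2.4 reports mean reductions above 70% in Phase 1 and predicts about 80% at steady state. It would be tempting to turn the counts into a bias and set it against the planned mNIS+7 effect. The documents give neither a split of exclusions by arm nor a difference between excluded and included patients, and mNIS+7 is not an affected endpoint, so no such figure is offered. This is a low-cost improvement, not a threat to the trial's main result.

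**What to change.** For TTR, RBP4, BMI, mBMI and NT-proBNP, define the analysis set as all randomised patients who received study drug and have a baseline and at least one post-baseline value of that endpoint, analysed as randomised. Compute the by-visit 60% TTR proportions in the same set. Keep the FAS for mNIS+7 and Norfolk QOL-DN, and leave the ECHO subgroup and CM-ECHO analyses of NT-proBNP as they are. If the FAS is to stay the main set for consistency with Protocol 10.3 and 10.5, add the endpoint-specific set as a prespecified supportive analysis beside it.

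The cost is SAP wording and one endpoint-specific population flag. No new data are needed, and the change can be made blind because the SAP is finalised before unblinding (SAP 2.6). Denominators will differ slightly between endpoints, which a table footnote can explain. Replacing the FAS would depart from the protocol and should be noted as such, as SAP 3.2.1 already does for the tertiary endpoints.
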